3.3. Changes made in the Statistical Analysis Plan

- Interim analysis 2 is added to the statistical analysis plan according to the changes made in protocol version 5.0.
- Patients who have usage of disallowed concomitant therapy or SLE standard of care therapy that deviate from the protocol will be considered as major deviations that

CONFIDENTIAL

The information contained herein may not be used, disclosed, or published without the written consent of Biogen MA Inc.

could impact the efficacy assessments and will be excluded from the per-protocol population (Part A and B).

- Failing Inclusion criteria 8.1.3 is now considered to impact the efficacy analysis.
- Endpoint ‘proportion of subjects with no worsening from baseline in subjects with lupus disease activity defined by <10% increase in PGA (VAS)’ is now changed to ‘by <1 point increase in PGA (VAS)’, so as the corresponding components in SRI-4, -5, -6 and BICLA.
- [REDACTED]
- [REDACTED]
- [REDACTED]
- [REDACTED]
- [REDACTED]
- Subgroup analysis will be modeled by MMRM model. To avoid inconsistency, if the MMRM model does not converge for some subgroups, ANCOVA model will no longer be performed for these same subgroups.

CONFIDENTIAL

The information contained herein may not be used, disclosed, or published without the written consent of Biogen MA Inc.

 Biogen	Statistical Analysis Plan 230LE201	<V 2.0>
--	---	----------------------

4. ANALYSIS POPULATIONS, STRATIFICATION FACTORS and VISIT DEFINITIONS

4.1. Definitions of Analysis Populations for Part A and Part B

Modified Intent-to-Treat (MITT) Population

The MITT population is defined as all randomized subjects who received at least 1 dose of study treatment (whether the subjects adhered to the protocol). Subjects will be analyzed according to the study treatment to which they were randomized. Analysis of other non-safety endpoints (e.g., demographics) will also be based on the MITT population.

Safety Population

The safety population will include the same subjects as defined for the MITT population. However, subjects will be analyzed by actual treatment received. If all subjects take the treatment as they were randomly assigned to, the safety population will be the same as the MITT population.

Per-Protocol (PP) Population

The per-protocol population will include the MITT subjects who do not have any major protocol deviations that could impact the efficacy assessments. Subjects will be analyzed by randomized treatment. Major deviations that could impact the efficacy assessments are:

Part A

- Actual treatment received is different from the planned treatment (e.g., patients received BIIB059 treatment while randomized to the placebo arm).
- Patients who have usage of disallowed concomitant therapy or SLE standard of care therapy that deviate from the protocol (specific rules for each concomitant therapy will be described in an addendum).
- Failing Inclusion/exclusion criteria that might potentially affect efficacy. The criteria listed in [Table 1](#) are considered not going to affect efficacy, thus they are not considered for per-protocol population.
- < 80% treatment compliance with study medication

CONFIDENTIAL

The information contained herein may not be used, disclosed, or published without the written consent of Biogen MA Inc.

- > 120% treatment compliance with study medication

Part B

- Actual treatment received is different from the planned treatment (e.g., patients received BIIB059 treatment while randomized to the placebo arm).
- Patients who have usage of disallowed concomitant therapy or SLE standard of care therapy that deviate from the protocol (specific rules for each concomitant therapy will be described in an addendum).
- Failing Inclusion/exclusion criteria that might potentially affect efficacy. The criteria listed in Table 1 are considered not going to affect efficacy, thus they are not considered for per-protocol population.
- < 80% treatment compliance with study medication
- > 120% treatment compliance with study medication

Table 1 Inclusion/Exclusion Criteria not Considered for Per-Protocol Population

Section in Protocol	Item	Affect Efficacy
8.1.1 Inclusion Criteria (Parts A and B)	1. Ability of the subject to understand the purpose and risks of the study and provide signed and dated informed consent and authorization to use confidential health information in accordance with national and local subject privacy regulations.	Not related to efficacy
	2. Age 18 to 75 years old, inclusive, at the time of informed consent.	Relaxed to age 12 to 80
	3. All women of childbearing potential and all men must practice effective contraception during the study and for 16 weeks after their last dose of study treatment.	Not related to efficacy
8.2.1 Exclusion	5. Other unspecified reasons that, in the opinion of the Investigator or Biogen, make the subject unsuitable for enrollment.	Not related to efficacy

CONFIDENTIAL

The information contained herein may not be used, disclosed, or published without the written consent of Biogen MA Inc.

Criteria (Parts A and B)	10. Subjects with a history of suicide attempt or suicidal ideation within 1 year prior to Screening.	Not related to efficacy
	13. History of severe herpes infection, such as herpes encephalitis, ophthalmic herpes, or disseminated herpes.	Not related to efficacy
	14. History of chronic, recurrent (3 or more of the same type of infection in a 12-month period), or recent serious infection (e.g., pneumonia, septicemia, herpes zoster) as determined by the Investigator and requiring anti-infective treatment within 12 weeks prior to Screening.	Not related to efficacy
	15. Signs of herpes or varicella zoster viral infection (specifically chicken pox, shingles, or herpes zoster) within 12 weeks prior to Screening.	Not related to efficacy
	16. History of or current diagnosis of active tuberculosis (TB), or untreated latent TB infection (LTBI), determined by a TB skin test with purified protein derivative as evidenced by induration ≥ 5 mm or a positive Quantiferon, positive or borderline T-SPOT (Elispot) test performed locally, either at Screening or documented with results within 12 weeks of the Screening Visit. Subjects who have previously completed appropriate and documented LTBI treatment will not be required to be tested. Subjects must have received complete LTBI treatment prior to Screening without evidence of re-exposure prior to entering the study. Subject with current household contacts with active TB will also be excluded unless the subject is being treated and there is evidence that household contacts are being treated. Indeterminate Quantiferon or T-SPOT tests may be repeated once and will be considered positive if retest results are positive or indeterminate. Subjects with documented BCG vaccination must perform a TB test at Screening and will be excluded if skin induration ≥ 5 mm or a positive Quantiferon or positive or borderline T-SPOT (Elispot) test.	Not related to efficacy
	18. Known hypersensitivity to BIIB059 or any of the components of the formulated BIIB059 or matching placebo.	Not related to efficacy
	19. History of, or ongoing, malignant disease, including solid tumors and hematologic	Not related to efficacy

CONFIDENTIAL

The information contained herein may not be used, disclosed, or published without the written consent of Biogen MA Inc.

	malignancies with the exception of basal cell carcinomas and squamous cell carcinomas and carcinoma in situ of the cervix that have been completely excised and considered cured >2 years prior to Screening.	
	21. History of substance abuse (except for cannabinoid) within 24 weeks prior to Screening, based on the Investigator's opinion.	Not related to efficacy
	22. Female subjects who are pregnant, currently lactating, have stopped lactating in the past 12 weeks, or are planning to become pregnant during the study and for 4 months after the last dose of study treatment.	Not related to efficacy

PK Population

The PK population will include the safety subjects who have at least one PK concentration measurement. Subjects will be analyzed by the actual treatment received.

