16.5. Safety

16.5.1. Analysis Population

For Part A and Part B, analysis of safety endpoints will be based on the safety population, defined as all subjects who received at least 1 dose of study treatment (whether randomized or not, or randomized in error). Subjects will be analyzed according to the study treatment actually received.

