16.5.2.1. Adverse Events

For Part A and Part B, AEs will be coded using the available, current version of the Medical Dictionary for Regulatory Activities (MedDRA). A TEAE will be defined as any AE that started or worsened in severity after initial dose of study treatment through the follow-up period; hereafter referred to simply as AE. AEs will be grouped by system organ class, preferred term, and overall, and then summarized. The incidence, severity, and relationship to study treatment will be summarized, separately for all AEs, treatment-related AEs, and SAEs.

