7. SAFETY ANALYSES

7.1. General Considerations

All safety analyses will be performed for the safety population. No statistical testing will be performed on the safety data.

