7.2. Analysis of Adverse Events (AEs)

All AEs will be coded by system organ class and preferred term using the MedDRA dictionary (Version 21.1 or the most updated version at data base lock). In this study, only treatment emergent AEs (i.e. those that occurred or worsened after the first randomized dose through the end of study) will be analyzed. Such AEs will have an onset date on or after the date of first randomized dose or will have presented prior to the first randomized dose and subsequently worsened. Therefore, whenever an analysis of summary of AEs is mentioned, it is intended that this is in reference to treatment-emergent AEs.

The number and percentage of subjects experiencing one or more treatment-emergent AEs in the following categories will be summarized.

- Any AE
- Any mild AE
- Any moderate AE
- Any severe AE
- Any related AE
- Any serious AE
- Any related serious AE
- Any AE that led to withdrawal of study drug
- Any AE that led to study withdrawal
- Any AE that led to drug interrupted, dose not changed
- Deaths

CONFIDENTIAL

The information contained herein may not be used, disclosed, or published without the written consent of Biogen MA Inc.

 Biogen	Statistical Analysis Plan 230LE201	<V 2.0>
--	---	----------------------

The following summaries will be presented.

- AEs by system organ class (SOC) and preferred term (PT)
- AEs by PT
- AEs by PT with an incidence of 5% or more in any of the treatment groups
- AEs by PT with at least 2% higher in incidence for either BIIB059 group compared to placebo
- Serious AEs by SOC and PT
- Treatment-related serious AEs by SOC and PT
- Severe AEs by SOC and PT
- AEs by relationship to study treatment by SOC and PT
- Treatment-related AEs by SOC and PT
- AEs that led to discontinuation of study drug by SOC and PT
- AEs that led to withdrawal from study by SOC and PT
- AEs by maximum severity by SOC and PT
- Suspected unexpected serious adverse reactions (SUSAR) by SOC and PT

To count the number of subjects who experience each AE, a subject experiencing the same AE multiple times will only be counted once for that preferred term. Similarly, if a subject experiences multiple AEs within the same system organ class, that subject will be counted only once for that system. For subjects experiencing the same AE more than once, the occurrence of the AE with the greatest severity will be used in the calculation of incidence by severity.

The following listings will be presented.

- Listing of serious AEs

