9.1. Immunogenicity Data

The analysis population for immunogenicity is defined as all subjects who are randomized and who have been dosed with study treatment and have at least 1 post-dose immunogenicity sample collected.

Summary of positive anti-BIIB059 serum antibodies will be presented by visits and by treatment group.

To define immunogenicity status the following rules will be used

- The baseline value is defined as the latest immunogenicity data collected at any time prior to the first dose. If no immunogenicity data are collected prior to the first dose, the baseline value is missing and will be imputed as anti-drug antibody negative for immunogenicity analyses.
- Subjects with at least one confirmed post-treatment positive result will be considered positive for anti-BIIB059 antibodies if their baseline result is negative.
- Subjects where none of the post-treatment samples were positive for anti-BIIB059 antibodies will be considered negative regardless of their baseline result.
- For subjects that are confirmed positive at baseline and have at least one post-treatment sample with a ≥ 4 -fold increase in titer will be considered positive for anti-BIIB059 antibodies. Subjects that are positive at baseline, with subsequent post-treatment samples titers that are within 2-fold will be considered negative for anti-BIIB059 antibodies.
- In addition, for subjects that are considered anti-BIIB059 antibody positive with final immunogenicity data, the following may be evaluated:
 - Persistence of the anti-BIIB059 antibody response: More than one positive evaluation that are ≥ 112 days apart or a positive evaluation at the last time point with no further samples available.
 - Transient anti-BIIB059 antibody response: A single positive evaluation or more than one positive evaluation <112 days apart.

The impact of anti-BIIB059 antibodies on PK parameters may be evaluated by considering antibody status (positive or negative, persistent/transient) as a co-variate in the analysis. The impact on efficacy may be evaluated by summarizing key efficacy endpoints by antibody status (positive or negative, persistent/transient). In addition, to determine the relationship (if any) of

CONFIDENTIAL

The information contained herein may not be used, disclosed, or published without the written consent of Biogen MA Inc.

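### The SAP safety population leaves out a subject who is dosed but never randomised, whom the protocol includes

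*SAP*

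**What the plan says.** Protocol Section 16.5.1 bases the safety analyses on "all subjects who received at least 1 dose of study treatment (whether randomized or not, or randomized in error", with each subject counted under the treatment actually received.

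SAP Section 4.1 ties safety to the efficacy set instead: "The safety population will include the same subjects as defined for the MITT population". The efficacy set is defined just above it: "The MITT population is defined as all randomized subjects who received at least 1 dose of study treatment". The SAP then adds: "However, subjects will be analyzed by actual treatment received".

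SAP Section 7.1 gives the definition its reach: "All safety analyses will be performed for the safety population".

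The two documents also start the clock for treatment-emergent adverse events differently. SAP Section 7.2 counts "those that occurred or worsened after the first randomized dose through the end of study". Protocol Section 16.5.2.1 counts "any AE that started or worsened in severity after initial dose of study treatment through the follow-up period". SAP Section 4.3 likewise defines baseline and treatment day from the first randomised dose.

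**The concern.** The protocol names subjects exposed without randomisation and puts them in the safety set. The SAP, which drives the programming, takes them out. If such an exposure occurred, the subject's adverse events, laboratory values, vital signs and ECG results would not appear in the study's safety outputs, contrary to the protocol. Changing the definition after the treatment codes are open, with a known case in hand, would look driven by the data.

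**Working it through.** No formula applies. This is a question of who belongs to each set, so the definitions are compared directly and then traced to the outputs.

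**Step 1: the sets.**
- Protocol safety set (16.5.1) = dosed.
- SAP safety set (4.1) = MITT = randomised and dosed.
- Difference = dosed and not randomised.

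**Step 2: case check.**
- Dosed, never randomised: in the protocol set, out of the SAP set.
- Randomised in error, then dosed: in both.
- Randomised, then given the wrong treatment: in both, counted under the treatment received.
- Randomised, never dosed: in neither.

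Only the first case is lost.

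**Step 3: does other SAP text bring that subject back?** The sentence on actual treatment in SAP 4.1 decides which group a subject is counted in, not whether the subject is counted. SAP Section 5.3 provides for repeat demographic tables if the safety and MITT populations differ, but the only difference it foresees is that some subjects do not get their randomised treatment. Nothing in the visible text restores a non-randomised subject.

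**Step 4: reach.** Through SAP 7.1 the exclusion applies to the adverse event tables and listings (7.2), laboratory tests (7.3), vital signs (7.4) and ECG (7.5).

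**Step 5: would changing the population sentence be enough?** Not clearly. A subject who was never randomised has no first randomised dose. Under SAP 4.3 that subject has no defined baseline or treatment day, and under SAP 7.2 no event of theirs qualifies as treatment-emergent. The protocol's anchor, the initial dose, works for everyone dosed. For a subject randomised before dosing, the usual case, the two anchors are the same date, so changing the anchor alters nothing.

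**Step 6: how many?** Neither document gives a count. Protocol Section 9.2 requires registration and randomisation through the IRT system before treatment starts, so the expected number is zero or very few. The documents offer no basis for a rate, and none is assumed here.

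**The case against.** The strongest case against acting is that the affected group should be empty, since the IRT requirement bars dosing before randomisation. That stands as a limit on size. It does not reconcile the documents, because the protocol's clause exists for the case where that safeguard fails.

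A reader might infer more than the documents support:

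- **That anyone dosed in error is lost.** The case check shows otherwise. Subjects randomised in error or given the wrong treatment remain in the SAP set.
- **That serious adverse events would go unreported.** Protocol Sections 15.3.2 and 15.3.3 require reporting within 24 hours regardless of any analysis population, and Section 19.2.1 provides for an independent committee to review interim safety data. The loss is confined to SAP outputs.
- **That the pharmacokinetic population departs from the protocol in the same way.** It does not. Protocol 16.2.1 draws that population from the ITT set, which Section 16.1.1 limits to randomised, dosed subjects.
- **That the immunogenicity population departs from the protocol.** SAP Section 9.1 starts from "all subjects who are randomized and who have been dosed with study treatment", but the protocol counterpart, Section 16.6.1, appears only in the contents list of the text available for this review. No conflict can be shown.
- **That the narrowing was made without being declared.** The readable parts of SAP 3.2 and 3.3 do not mention it, but both sections are partly redacted, so a declaration or rationale cannot be ruled out.

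**Conclusion.** The point holds in a narrow form. SAP 4.1 contradicts protocol 16.5.1 for subjects dosed and never randomised, and any such subject would be missing from every SAP safety table and listing. If there are none, no result changes. If there is one, that subject's safety data are left out contrary to the protocol. This is a minor alignment correction with no bearing on efficacy, sample size, power or error control. The conclusion rests on the visible text. A rationale under the redaction in SAP 3.2 might explain the narrowing, but the two definitions would still differ.

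**What to change.** 1. In SAP 4.1, restore the protocol's safety population: everyone given at least one dose of study treatment, with or without randomisation, analysed by treatment actually received. Adjust SAP 5.3 so that the repeat demographic tables are also triggered when the two populations differ in membership.
2. For safety analyses, replace the first randomised dose with the first dose of study treatment in SAP 4.3 and 7.2, consistent with protocol 16.5.2.1. Efficacy definitions can stay as they are.
3. In SAP 4.1, draw the pharmacokinetic population from the MITT subjects. It is now drawn from the safety subjects, so step 1 alone would admit non-randomised subjects and create a new departure from protocol 16.2.1.
4. Check SAP 9.1 against protocol 16.6.1 and change it only if they differ.

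If the narrower population is intended, the alternative is to state and justify it in SAP 3.2. Either way, the change is best made before unblinding. The cost is a few sentences and the matching safety-population and treatment-emergent flags in the programs.

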4.2. Stratification Factors

The randomization stratification used for both Part A and B under each protocol versions (PV1 and PV2) is shown below:

Part A

PV1

- Oral Corticosteroid Usage (≤ 10 mg/d vs. > 10 mg/d)
- CLASI-A score (≤ 10 vs > 10)

PV2 (or later)

- Oral Corticosteroid Usage (≤ 10 mg/d vs. > 10 mg/d)
- Geographic Region (United States vs. Asia vs. Latin America and Europe)

Part B

PV1

- CLASI-A score (≤ 10 vs. > 10)

CONFIDENTIAL

The information contained herein may not be used, disclosed, or published without the written consent of Biogen MA Inc.

 Biogen	Statistical Analysis Plan 230LE201	<V 2.0>
--	---	----------------------

- SLE (Yes/No)

PV2 (or later)

- CLASI-A score (≤ 10 vs. > 10)
- DLE (Yes/No)

4.3. Visit/Analysis Week Definitions

The definition of visits below applies to both parts A and B.

Baseline

Baseline will refer to the last non-missing value prior to the first randomized dose.

Treatment Day [TD] (Days relative to the first randomized dose)

To facilitate the analysis of the data in the treatment period (TP), TD will be calculated for each day in the study as the number of days between the date of the first randomized dose and the specific day of interest. For a day that is on or after the day of the first randomized dose, the TD is a positive value and will be calculated as (date of study day – date of the first randomized dose +1). For a day that is prior to the date of the first randomized dose, the TD is a negative value and will be calculated as (date of study day – date of the first randomized dose). The study starts at TD1.

Analysis Week

Observations that are collected after the first randomized dose as scheduled visit will be used to the corresponding analysis week. Baseline corresponds to “Week 0” in the protocol or the latest non-missing value prior to first study drug administration if Week 0 assessment is missing.

Data from Early Termination or Unscheduled Visits

In general, when data are summarized by visit/analysis week, the Early Termination Visit or Unscheduled Visit will be assigned to an appropriate scheduled visit/analysis week (PV2 or later) by using a window scheme as follows.

CONFIDENTIAL

The information contained herein may not be used, disclosed, or published without the written consent of Biogen MA Inc.

The lower bound and the upper bound for the visit windows are defined as the midpoints of the scheduled visits (PV2 or later). If the date and time from early termination visit falls in between the lower bound and the upper bound for a scheduled visit, then it will be assigned to that visit. If there are 2 or more assessments available in the same analysis window for a subject, the assessment that is closest to the target visit day will be used for analysis. If there are 2 or more assessments in the same analysis window with the same distance from the target visit day, the earlier assessment will be used.

The windowing scheme for the primary endpoint in Part A and Part B is shown in [Table 2](#) and [Table 3](#) below.

CONFIDENTIAL

The information contained herein may not be used, disclosed, or published without the written consent of Biogen MA Inc.

Table 2 Visit Windows for Primary Endpoint (Joint Count) in Part A

Analysis visit	Target visit day	Analysis visit window
Baseline (Week 0)	1	Most recent non-missing pre-dose value
Week 2	15	[2, 22]
Week 4	29	[23, 43]
Week 8	57	[44, 71]
Week 12	85	[72, 99]
Week 16	113	[100, 127]
Week 20	141	[128, 155]
Week 24	169	[156, 197]
Follow-up 12	253	≥ 198

Table 3 Visit Windows for Primary Endpoint (CLASI) in Part B

Analysis visit	Target visit day	Analysis visit window
Baseline (Week 0)	1	Most recent non-missing pre-dose value
Week 2	15	[2, 22]
Week 4	29	[23, 43]
Week 8	57	[44, 71]
Week 12	85	[72, 99]
Week 16	113	[100, 141]
Follow-up 12	197	≥ 142

*For Part B subjects in PV1 who didn't reconsent to PV2 and hence don't have week 16 visit, the follow-up period days and lower and upper bound of visit window will shift back by 28 days

CONFIDENTIAL

The information contained herein may not be used, disclosed, or published without the written consent of Biogen MA Inc.

